Summary of Pilot Study: The pilot EAW study using the ReWalk performed at the JJPVAMC trained 12 participants in the ReWalk exoskeleton for a combined total time of >1200 hours. EAW of four to six hours per week was well-tolerated by the participants. Time in the exoskeleton resulted in improved skill level. One-half of the participants reported clinically significant improvements in bladder and bowel function and reduction in pain outcome measurements. There were no study-related serious adverse events (SAEs). Skin abrasions at the points of contact with the device occurred across 9 of the 12 participants; these were reported as “study-related adverse events.” All skin abrasions were resolved with adjustments in padding and fit of the device to the participants. One participant fell due to slipping on a wet floor, but was not injured. These adverse events were consistent with those reported by others for exoskeletal-assisted walking [43, 44, 83].

II. OBJECTIVES

The short-term aims are to demonstrate in Veterans with SCI who are wheelchair users for indoor and outdoor mobility the efficacy for changes in QOL, improvements in body composition and the safety of home/community use of a powered exoskeleton for ambulation.

The long-term aims are to share the knowledge gained from this research study with the Department of Veterans Affairs (DVA) Veterans Health Administration (VHA) Spinal Cord Injury Patient Care Centers' clinical staff about the training procedures, education of and the development of guidelines for the clinical prescription of the exoskeletal-assisted walking device for home/community use in Veterans with SCI.

The study sample size is powered from preliminary data for the two primary outcomes [Mental Component Summary (MCS) of the Veterans Rand-36 (VR-36) and Spinal Cord Injury Quality of Life (SCI-QOL) assessment tool] and the major secondary outcome (total body fat mass). The secondary outcomes are exploratory and will not be used to power the study sample size.

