As with any clinical trial, the safety of the participants will be of utmost concern. Safety will be monitored closely and data will be collected on adverse events (AEs) and serious adverse events (SAEs) throughout the course of the study. All AEs and SAEs will be systematically recorded on case report forms and coded by the CSP Clinical Research Pharmacy Coordinating Center (CSPCRPCC) at Albuquerque using the MedDRA system. The MedDRA system employs standard terminology to present adverse events and to organize them by body system. The incidence of adverse events will be summarized for each treatment group and overall by body system and MedDRA preferred term. The incidence differences between the control and intervention groups for each event will be tested using the Pearson chi-square test or Fisher’s Exact test. Table 17 illustrates how AE data may be presented for this study.

Table 17. CS #2003 Cumulative Incidence of Adverse Events by Body System and MedDRA Term

Body System and Preferred Term	SOC (n = ?)	EAW + SOC (n = ?)	All Participants (N = ?)	p-value
	n (%)	n (%)	n (%)	
All Adverse Events				
Subjects with at least one Adverse Event				
Body System 1				
Event 1				
Event 2				
Event 3				
.				
.				
.				
Body System 2				
Event 7				
Event 8				
Event 9				
Event 10				
.				
.				
.				
Body System N				
Event 14				
Event 15				
Event 16				
.				
.				
.				
Event N				

It is the responsibility of the CSPCC Study Team to provide the DMC with whatever information they feel they need to successfully monitor the study. Thus, additional tables will be added as required. In addition to the reports for the yearly meetings, the DMC will also be provided with reports between meetings at 6-month intervals.

XIV. QUALIFICATIONS

A. Site Qualifications

The Site Investigator is required to be a SCI staff physician. S/he will be responsible for the initial
 CSP #2003
 Exoskeletal Assisted Walking with Persons with SCI: Impact on Quality of Life (PEPSCI)
 Version 7.2 Protocol July 2021

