in this study. A small stipend of \$30 per visit to the SCI Centers has been included in the budget to help defray some of the expense and inconvenience of travel for participants in this study. During Screening, stipends will be given for up to 3 visits for screening/baseline evaluations (max. \$90) and up to 5 days for EAW basic training (max. \$150). At JJPVAMC, during the pilot study, it was found that participants were highly motivated to attend the 3 times weekly exoskeletal-assisted walking sessions and compliance was greater than 90%. Reimbursement for transportation and lodging may be made available to participants and companions who live more than 45 miles away from the SCI Centers. The amount will vary based on distance and will be arranged in advance with the study team.

E. Safety Considerations

Trainers will be able to identify symptoms and signs of autonomic dysreflexia (AD), such as rapid increase in blood pressure, flushing in the face, sweating above the level of injury; or symptoms of orthostatic hypotension, such as paling of the face and participant reporting lightheadedness. Study Trainers will have a policy in place at their facility in order to address these types of emergencies. These policies should include a place where the participant can be brought to a sitting position or safely laid down on the floor. Once they are in a safe position, the cause of the problem can be assessed, and appropriate steps can be taken. If there is an “error” in the ReWalk device, the Trainers will assist the participant to a sitting position using the graceful collapse feature. It will be strongly recommended that participants receiving anticoagulation therapy wear a helmet during use of the exoskeleton.

F. Foreseeable Risks

The potential risks associated with having a person with SCI dynamically load in an upright position and walk overground with a powered exoskeleton include: hypotension, low-impact fracture, falls resulting in bone fracture, muscle soreness or tear, joint damage, or other musculoskeletal injury, skin breakdown, and/or AD.

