All potential participants will be examined and their medical charts will be reviewed by the study team physician (who is also a member of the study site’s medical center staff) before being cleared for participation. Study personnel will be in attendance at all times while a participant is using the exoskeleton and while all testing is being performed. Blood pressure and heart rate will be monitored before, during, and after the training sessions, primarily to identify changes in blood pressure. The study staff will query the participants throughout each session for early signs or symptoms of hypotension such as feeling light headed or queasiness. During the sessions, persons with a fall in blood pressure from their pre-session seated BP of $>20/10$ mmHg will be seated or brought to a supine position. The staff involved with this study will be trained to look for signs and symptoms of AD. Most persons with SCI are also knowledgeable about AD, but all participants will also be made aware of these signs and symptoms of AD. The legs where the straps are fastened will be examined for skin breakdown during (as needed) and after training sessions to ensure that there are no areas that may be abrading. If evidence of skin redness,

irritation or breakdown exists, alternate placements for straps and/or padding will be used to protect the area. Participants who have continued breakdown will be temporarily discontinued. Participants will be checked after each session for signs of edema. If edema is present, participants will be instructed to elevate their feet, use compression socks for the next session, and/or reduce the upright time or training frequency. If edema persists more than one day, the participant will be referred to the Site Physician. Training sessions will be discontinued if need be.

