The ReWalk powered exoskeleton has safeguards built within the device to prevent or minimize injury to the user. The system can detect if there is a mechanical or electrical problem and automatically causes the device to remain in the standing position, preventing the user to walk in the system. The only movement the device will be able to do is sit down so that the user can be removed from the system safely. If there is a mechanical error while in the sitting position, the device will not allow the user to stand in the system, and there will be a sound alerting the person that there is a problem. If there is a sudden loss of power while standing or walking, there is a safety mechanism that will stiffen the joints of the exoskeleton passively and cause the joints to rotate slowly so that the person can have a “graceful” collapse to the floor without causing them harm. The “graceful” collapse function allows time for a protective response with the arms to reach for the ground. The ReWalk exoskeleton is instrumented with two power sources; one main battery which has power for up to 4 hours of continuous walking and an additional back up battery which has power for up to an additional 30 min of walking. The participant, companion and study team members will be instructed to ensure that the power source of the system is fully charged prior to any use of the ReWalk.

To prevent tripping over obstacles, the areas used for the sit-to-stand, stand-to-sit, walking, and stepping will be checked before and during each session to be free of any obstacles and water on the floor. There are risks associated with anticoagulation therapy if a participant were to fall and hit their head. It will be strongly recommended that participants receiving anticoagulation therapy wear a helmet during use of the exoskeleton. To prevent a potential fall, participants will not be progressed to walking until they have mastered the basic skills set. Additionally, all participants will be spotted by at least one study team member (and/or their companion once trained) while using the ReWalk and never left unattended.

Additional efforts to minimize the risk of fracture will be done by excluding those veterans with BMD in the extremely low range. Measurement of the BMD is part of the screening and eligibility criteria for participation in this study. Those potential participants who have low bone mass will

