In addition to having a truly immediate translation to clinical care, our study will actually make possible the clinical use of the exoskeleton by training local professional staff to become sufficiently skilled in the training of Veterans and military members with SCI who wish to use this technology for upright ambulation. In summary, clinical staff at the study sites will have the opportunity to directly participate in exoskeletal training, which will provide hands-on experience that will be readily transferrable to clinical care. This study will provide important clinical information, such as who are the best candidates for home use of an exoskeleton, the average number of sessions needed to pass the advanced skills test, the level and completeness of SCI that is related to successful use of the device, how often and in what locations the exoskeletons should be used, and any unexpected adverse events or serious adverse events, if they should occur, associated with home use. The prosthetics and orthotics departments will gain the opportunity to learn about the system and how to fabricate additional padding, if needed, for participants in addition to setting up contracting for purchasing these types of devices. There are other exoskeletons which will become available. The experience that the facilities gain from participation in this study will be a basis to identify the important features these new systems may offer to improve clinical care provided to veterans with SCI. Perhaps most importantly for the

clinical services, is the question of there being unexpected adverse events or serious adverse events associated with home use as well as how much is this device actually being used in the home/community environment.

XX. IMPACT OF THE SARS-COV-2 (COVID-19) PANDEMIC ON VETERANS WITH SPINAL CORD INJURY

This section has been added to the protocol to identify the impact of the COVID-19 pandemic on the screened participants from CS #2003. The questions to be asked are unrelated to the original research design and outcomes of CS #2003. A baseline questionnaire will be completed with screened participants as well as a follow-up questionnaire and a blood draw. These additions are at no additional cost to the study. All costs will remain budget neutral within each site. Although a budget for each site will be provided, it is understood that each site will cover these costs within the approved budget for their site.

A. Background

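### Harms are compared by one test per adverse event, with no pre-specified between-arm estimate and interval for fracture or falls

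*Combined protocol and SAP*

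**What the plan says.** All references are to the combined protocol and SAP.

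- **Analysis of harms (XIII.I).** Adverse events are MedDRA-coded, and "The incidence of adverse events will be summarized for each treatment group and overall by body system and MedDRA preferred term". For the comparison of arms, "The incidence differences between the control and intervention groups for each event will be tested using the Pearson chi-square test", with Fisher's exact test as the alternative. No rule says which of the two applies when, and no significance level is given for these tests.
- **Display (XIII.I, Table 17).** The columns are n (%) by arm and overall, and a p-value. The rows are all adverse events, subjects with at least one event, body systems, and single events. The table is offered as an illustration. On what the Data Monitoring Committee (DMC) may ask for, the plan says: "Thus, additional tables will be added as required".
- **Named harms (XVIII.F).** The foreseeable risks are "hypotension, low-impact fracture, falls resulting in bone fracture, muscle soreness or tear, joint damage, or other musculoskeletal injury, skin breakdown, and/or AD".
- **Why they matter to this trial.** The short-term aims in section II include "the safety of home/community use of a powered exoskeleton for ambulation". On fracture, XVIII.G says: "Additional efforts to minimize the risk of fracture will be done by excluding those veterans with BMD in the extremely low range". Section VIII.B also excludes people with a fragility fracture of the lower extremity since injury.
- **Reporting (XVII.B).** The primary paper will report adverse events; no method is given.

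**The concern.** Someone deciding whether to prescribe the device for home use will want to know how many participants in each arm had a fracture or a fall, and how large the difference could plausibly be. The plan commits to a count and a p-value for each coded event. It does not commit to a count of participants with any fracture or any fall, to a difference between arms, or to an interval.

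The rows that are planned do not fill the gap. The all-event and body-system rows mix fractures and falls with other events. A preferred-term row may be narrower than the harm itself. For a rare harm at this sample size, a non-significant p-value is easily misread as reassurance, and a significant one may depend on the test chosen. Participants and staff know who has the device, so a grouping or test chosen after arm-level data have been seen is open to challenge.

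**Working it through.** **Inputs from the plan.** 80 per arm (XIII.B) and two-sided tests (XIII.E). As a check on the 80: the continuity-corrected two-proportion formula at two-sided 0.025 reproduces Table 7's 67, 60 and 66 per group. Dividing by 0.85 gives 78.8, 70.6 and 77.6, which round up to the stated 79, 71 and 78.

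**Assumptions.** The documents give no comparative fracture or fall rate, no level for adverse event tests and no list of preferred terms. The event counts, rates, term splits and 0.05 level below are illustrative, and all 80 participants per arm are taken as evaluable.

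**Step 1. Formulas for x events in the device arm and none in the control arm.**
- Fisher, two-sided: p = 2 × C(80,x) / C(160,x). For x=4: 2 × 1,581,580 / 26,294,360 = 0.120.
- Pearson, uncorrected: X² = 160x / (160 − x). For x=4: 640/156 = 4.10, p = 0.043.
- Risk difference: x/80, with a Newcombe interval built from the Wilson limits of each arm. For x=4 the Wilson limits are 1.96% to 12.16% and 0% to 4.58%. The lower limit is 5.0 − √((5.0 − 1.96)² + 4.58²) = −0.5 points, and the upper limit is 12.2.

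| Events | Fisher p | Pearson p | Difference, points (95% CI) |
|---|---|---|---|
| 2 v 0 | 0.50 | 0.15 | 2.5 (−2.4 to 8.7) |
| 4 v 0 | 0.12 | 0.043 | 5.0 (−0.5 to 12.2) |
| 6 v 0 | 0.028 | 0.013 | 7.5 (1.4 to 15.4) |

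At 4 v 0 the two permitted tests fall on opposite sides of 0.05. The estimate and its interval do not depend on that choice.

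**Step 2. Term splitting, if it occurs.** Suppose six fractures are coded 2/2/2 over three preferred terms. Each row then reads as the 2 v 0 line (Fisher p=0.50, Pearson p=0.15), while the grouped row reads as the 6 v 0 line.

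**Step 3. Power.** Grouped power is by exact enumeration. Power for at least one significant preferred-term row, with three equal terms, is by multinomial simulation (400,000 trials). Body-system and any-event rows are not counted in the comparator.

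| True rates, device v control | Grouped: Fisher / Pearson | Any of three terms: Fisher / Pearson |
|---|---|---|
| 10% v 1% | 62% / 75% | 12% / 53% |
| 5% v 1% | 11% / 30% | 0.5% / 10% |
| 3% v 0% | 3% / 22% | under 0.1% / 3% |

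Grouping helps in each case, and less under Pearson. At the two lower rates the grouped test is itself weak, so the interval is the useful output.

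**The case against.** The strongest reply has four parts.

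1. **Term splitting is assumed.** This stands. Nothing in the documents shows fractures or falls being coded to several terms. If each is one term, Table 17 already gives counts by arm. Even so, it would give only n (%) and a p-value, so the missing interval does not depend on splitting.

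2. **The large power contrast needs a high rate.** This also stands. A 10% rate means about 8 fractures in 80 people already screened on bone density and fracture history. The 12-person pilot had no study-related serious event and one uninjured fall. That is too few to fix a rate, but it lends no support to 10%.

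3. **The plan is flexible, and an any-fracture count could be derived from the coded data.** True. But the provision for extra tables serves the DMC, names no grouping and does not fix the final analysis.

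4. **A list of foreseeable harms does not answer the question in section XIX**, which for the clinical services "is the question of there being unexpected adverse events or serious adverse events associated with home use". This is fair: the two rows serve the aim in section II and the risks in XVIII.F, not the search for unexpected events. XVIII.F also names falls only where they cause a fracture. Any fall is still a sensible row, since XVIII.G describes measures to prevent falls in general.

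A reader might go further and infer that a fracture signal would be hidden, or that grouping would reliably find one. The documents and figures support neither. Individual events appear by arm, serious events are reported and summarised for the DMC, and grouped power is low at low rates. Nor is there a detection problem for skin breakdown: at an assumed 50% v 5%, at least one term row is significant with power of at least 99.9% under either test for every split tried.

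**Conclusion.** The point holds as a gap in estimation. The plan fixes a test for each event but no per-participant between-arm estimate with an interval for fracture or falls, although safety in home use is a stated aim and fracture risk shapes eligibility. The part that does not rest on term splitting is the dependence on test choice and the missing interval: at 4 v 0 the p-value is 0.12 or 0.043, against one difference of 5.0 points (−0.5 to 12.2). The dilution argument is conditional on fractures being coded to several terms. All event counts and rates are illustrative, and the 0.05 level is assumed. The primary and major secondary analyses and the sample size are unaffected. Priority is low; the case for acting is that the change costs almost nothing.

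**What to change.** In XIII.I, before final data review, add two grouped rows to the adverse event analysis: any fracture and any fall. List the terms that make up each, and state whether a fall without injury counts. Count each participant once per row, and report n (%) by arm with the risk difference and a score or exact 95% CI. Keep the preferred-term rows as supporting detail.

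Grouped rows for the other harms in XVIII.F are optional. If skin breakdown is added, show it as an estimate only, because detection differs by arm: at training, which only the device arm continues after randomisation, "The legs where the straps are fastened will be examined for skin breakdown during (as needed) and after training sessions" (XVIII.G). Leave out a split into fragility and traumatic fractures unless the mechanism of injury is recorded. The content listed for serious event reports in XI.F does not mention it, and the definitions in VIII.B are open-ended.

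The cost is some SAP wording, a short term list and two table rows, using events already collected (XI.E) and coded (XIII.I). The downside is that intervals for rare harms will be wide.

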The Orientation/Training phase is performed in the hospital or in the participant's home/community. Participants in the Intervention group will be required to meet with the study team for 3 to 5 sessions per week for 20 to 30 sessions. Participants who miss sessions will be contacted by the Site's Study Coordinator or ReWalk Trainers for rescheduling. During the Intervention phase, the participants will be using the exoskeleton in their home/community. During this phase, follow-up contact by the study team members with the participants on a weekly basis will be critical for compliance and troubleshooting of any problems. This contact will be necessary to assist the participants with compliance of completion of the Usual Activity Log and the EAW Activity Log and identification of adverse events in the Intervention group. Contact will be made in person, over the phone, or through secure messaging, using My HealtheVet.

During the Orientation/Training phase, the Control group will make weekly outpatient visits and/or receive contact from members of the site's study team on a weekly basis. During the Intervention phase, follow-up contact by the study team members with the participants in the Control group will be at a minimum of one time weekly. This contact will be critical for compliance of completion of the Usual Activity Log and identification of adverse events in the Control group. Site team members will be instructed in the weekly and monthly participant contact procedures for both groups to collect data, encourage compliance, and identify issues. Contact will be made in person, over the phone, or through secure messaging, using My HealtheVet.

Primary and Secondary outcome assessments will be completed at the SCI Centers at the end of month 2 and month 4 of the Intervention phase in both groups.

VII. METHODS OF ASSURING UNIFORMITY OF INTERVENTION

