Any Serious Adverse Event (SAE) is reported on both the SAE and AE case report forms. The Site Investigator will be responsible for reporting a SAE, ascertaining the participant's study identification number, date of event, and will determine if the SAE is related, possibly related or not related to the protocol. A description of any outcome or response to the SAE will also be included in this report. As more information about a SAE becomes available, updates to this initial report must be made on the SAE Follow-Up form. It is the responsibility of each Site Investigator to report SAEs from their site to the CIRB within the timelines they require. SAE data are tabulated by the CSPCC at [name] and the CSPCRPCC at Albuquerque, NM, and summarized and in the report to the DMC. ReWalk Robotics, Inc. will be provided a summary of SAEs annually.

G. Adverse Event (AE) and Unanticipated Adverse Device Effect (UADE) Reporting

Any mild (awareness of symptom, but easily tolerated), moderate (discomfort enough to cause interference with usual activity) or severe (incapacitating with inability to work or do usual activity) AE must be reported on the AE case report form. Any AE which also meets the criteria for a SAE must also be reported on the SAE form. It is the responsibility of each Site Investigator to report AEs from their site annually to the CIRB. Participants will be monitored at a minimum of one time per week for AEs and recorded on the appropriate form should any occur. AE data are tabulated by the CSPCC at [name] and the CSPCRPCC at Albuquerque, NM and summarized in the report to the DMC.

UADEs must be reported by the clinical investigator to the sponsor and the CIRB, Investigators are required to submit a report of a UADE to the sponsor and the reviewing IRB as soon as possible, but in no event later than 10 working days to the sponsor and no later than 5 days to the CIRB after the investigator first learns of the event. This reporting will be to the CSP Clinical Research Pharmacy

Coordinating Center on an AE or SAE form, as appropriate, and to the CIRB on the relevant IRB form. The reporting period for UADEs begins when the participant signs the informed consent form and continues until the participant's completion or early termination of participation or the end of the study

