As part of the orientation and training for each participant on the device, the expected occurrence of routine AEs will be described to the participants, including that they may experience skin abrasions, and hand, shoulder or any other joint discomfort. During the five-session Basic Training and in the Screening Phase and the Orientation/Training Phase, participants will be asked during each session if they are experiencing any discomfort or pain. Hand or shoulder discomfort, if they occur, are expected to occur early on in training when the participant is learning to use the device. Participants who report any pain or other medical problem will be referred to the Site physician. The Site physician will be responsible for taking the appropriate course of action for the AE or SAE. The study staff will be responsible for recording the occurrence of AEs or SAEs appropriately, as they occur. Additionally, the SMART unit will be charged with monitoring the informed consent documentations, source documents, AE and SAE forms, as well as assessing if the Site study team is carrying out the study correctly.

The Site Investigator will be responsible for monitoring these events on a regular basis at his/her site. The immediate and ongoing safety review of study data to monitor for evidence of adverse events will be conducted by the Cooperative Studies Program Clinical Research Pharmacy Coordinating Center (CSPCRPCC) in Albuquerque, NM. The Data Monitoring Committee (DMC) will review AEs and SAEs on a regular basis.

H. Participant Safety Stopping Rules

The Site Physician will make the decision for participants who have a safety or medical concern such as: skin breakdown, edema, joint discomfort, muscle soreness, extreme fatigue, or any other medical condition as to whether they are to be continued as is, continued with modifications to the equipment, temporarily discontinued, or withdrawn from the study. Re-entry to the Training or Intervention phases of the study will be based on the Site Physician's medical clearance and the participant's safety to begin again.

I. Site Participation Stopping Rules

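### In Orientation/Training, adverse events are looked for harder in Intervention than in Control, and the SAP's between-arm test of every event term makes no allowance for this

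*Combined protocol and SAP*

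**What the plan says.** **The test.** Section XIII.I (DMC monitoring) summarises adverse events by arm, body system and MedDRA term, and states: "The incidence differences between the control and intervention groups for each event will be tested". The methods named are chi-square (Pearson) and Fisher's exact. Table 17 is headed as cumulative incidence and has a p-value column. The section has no split by phase, no separation by how an event was found, and no caveat about unequal ascertainment. It gives no significance level for these tests.

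**Intervention arm, Training.** Section VI schedules "3 to 5 sessions per week for 20 to 30 sessions". Section XI.G says that "participants will be asked during each session if they are experiencing any discomfort or pain". Section XVIII.G adds that the legs at the straps "will be examined for skin breakdown during (as needed) and after training sessions", and that "Participants will be checked after each session for signs of edema".

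**Control arm, Orientation.** Sections VI and VIII.I give Control weekly visits and/or weekly contact, which may be in person, by phone or by secure message. No skin or edema check is specified. The general floor in Section XI.G, for everyone, is to be "monitored at a minimum of one time per week for AEs".

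**Common to both arms.** The five basic training sessions come before randomization and apply to everyone. In the four-month Intervention phase, Section III.B schedules weekly contact and a similar amount of attention in both arms.

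**The concern.** Section XI.G puts even mild events on the AE form. Whether a mild, short-lived event is recorded depends on how often someone asks or looks. Chronic pain is described in Section I as common in this population whatever the treatment, and swelling or skin redness can also occur without the device. If one arm is asked and examined several times a week and the other is contacted once, a difference in recorded incidence can arise with no difference in risk.

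Safety of home and community use is a stated aim (Section II), and the AE table goes to the DMC. A small p-value for a background term would be hard to read. It could reflect device harm, closer looking, or both.

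**Working it through.** **1. The plan's own figures.** The documents give no figure for AE ascertainment or AE power. The 80 per arm used below comes from Table 7, which reproduces exactly with the continuity-corrected two-proportion formula at two-sided 0.025, then division by 0.85: 67 → 79 (10% v 33.3%, 80% power), 60 → 71 (10% v 42%, 95%), 66 → 78 (10% v 35%, 85%).

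**2. Scheduled contacts after randomization.**
- Training, Intervention: 20 to 30 sessions.
- Orientation, Control: about 12 weekly contacts on Table 6 (weeks 5 to 16), ratio 20/12 to 30/12 = 1.7 to 2.5. If the two-month Orientation in Section III.D applies, about 8 contacts, ratio 2.5 to 3.75. Section III.D gives Training three months and Orientation two, while Table 6 shows the same weeks for both; these passages must be reconciled.
- Adding about 17 weekly contacts per arm for the four-month phase: (20+17)/(12+17) = 1.3 to (30+17)/(12+17) = 1.6. With 8 Orientation weeks: 37/25 = 1.5 to 47/25 = 1.9.

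The asymmetry is therefore marked in Orientation/Training and diluted over the whole follow-up.

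**3. Effect on the test: an illustration.** Assumptions not in the documents:
- true incidence *p* is equal in both arms, 30% or 20%;
- Intervention captures every event;
- Control captures a fraction *c* of these during Orientation/Training and all of them afterwards;
- a share *f* of the hazard falls in Orientation/Training.

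Recorded Control incidence is

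p_C = 1 − (1 − p)^(1 − f(1 − c)).

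With constant hazard, f = 12/29 = 0.414. At p = 0.30 and c = 0.60 the exponent is 1 − 0.414 × 0.40 = 0.834, so p_C = 1 − 0.70^0.834 = 0.257. For c = 0.90 and 0.75, p_C is 0.290 and 0.274.

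Two Binomial(80) arms were enumerated exactly with the uncorrected Pearson chi-square, counting rejections with Intervention higher. Chance of a false Intervention excess, per term:

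| Case | c = 100% | 90% | 75% | 60% |
|---|---|---|---|---|
| p = 30%, f = 12/29, two-sided 0.05 | 2.6% | 3.6% | 5.7% | 8.9% |
| p = 20%, f = 12/29, two-sided 0.05 | 2.5% | 3.3% | 4.8% | 7.0% |
| p = 30%, f = 0.70, two-sided 0.05 | 2.6% | 4.4% | 9.5% | 18.6% |
| p = 30%, f = 12/29, two-sided 0.01 | 0.5% | 0.7% | 1.3% | 2.3% |
| p = 30%, f = 12/29, Fisher's exact, 0.05 | 1.7% | 2.3% | 3.9% | 6.2% |

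The third row covers events that cluster in training. The 0.01 row uses the level that Section XIII.E sets for other secondary outcomes, since none is given for AEs.

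**The case against.** The strongest reply has five parts.

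- **The imbalance is limited in time.** This stands. A reader might infer that Control is under-observed throughout. Applying the capture loss to the whole follow-up (recorded Control incidence 27%, 22.5% or 18% against 30%) gives false-excess rates of 6%, 19% and 44%. The documents do not support that: Section III.B schedules similar contact in the four-month phase, and the pre-randomization sessions are common to both arms.
- **The data may already allow separation.** A reader might also infer that the two sources of difference can never be untangled. That cannot be known. The AE form and the procedures manual are not in the documents, onset dates may be recorded, and Section VI mentions contact procedures taught for both groups. Section XIII.I also allows extra DMC tables. What stands against the plan is that it specifies neither a common question set nor a split.
- **No decision hangs on these p-values.** Correct. No stopping rule uses them; safety decisions rest on DMC judgment. The bias also runs against the device, so it does not hide harm. It can still misattribute harm.
- **Session checks are inherent to device use and find real harm.** Also correct. The pilot saw skin abrasions in 9 of 12 participants. Removing session-found events from the comparison altogether would delete true device events from one arm only, so the full table has to stay.
- **It is late.** The text is Version 7.2, July 2021, and Table 5 ends enrollment in FY20. A new form field cannot help participants already followed; a phase split can.

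**Conclusion.** The concern holds for Orientation/Training and for mild, non-serious events that Control participants could also have. In that phase ascertainment differs by design, and the SAP's cumulative test ignores it. SAEs are little affected.

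The direction is towards an apparent Intervention excess, whatever capture fraction is assumed. The size is not derivable from the documents. Under evenly spread events and the assumptions above, inflation is modest: at most 8.9% against 2.6% per term at 30% incidence, and 7.0% against 2.5% at 20%. Clustering in training raises it (18.6% in the example shown); a 0.01 level lowers it. Incidence, capture fractions, hazard split and significance level are all assumptions.

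The finding does not show that an observed excess would be an artefact. It shows that the planned p-value could not tell device harm from closer looking.

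**What to change.** **Section XI.G.** Use one identical, fixed AE question set at the weekly contacts that already take place in both arms. Record on the AE form how each event was found (weekly questions, session check, spontaneous report, visit), allowing more than one source. Leave all session checks unchanged.

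**Section XIII.I.**
- Keep the full all-event Table 17 by arm. Label its p-values descriptive and affected by unequal ascertainment.
- Present AEs separately for Orientation/Training and for the four-month Intervention phase.
- Base between-arm inference for non-serious events on the four-month phase and on events from the common weekly questions.
- Report all session-detected events in full for Intervention.

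**Cost.** One form field, one question list used in existing contacts, and one extra table. The commonly ascertained comparison may miss some device events, which is why the full table stays. Frequent questioning at sessions may also prime answers to the weekly set, so the bias is reduced rather than removed. The source field works only for participants followed after the change; the phase split needs only onset dates.
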